9.2.2.2 Reporting Procedures for Serious Adverse Events

The investigator is responsible for ensuring that all serious adverse events observed by the investigator or reported by the subject that occur after signing of the ICF through 90 days following cessation of treatment, or 30 days following cessation of treatment if the subject initiates new anticancer therapy, whichever is earlier, are recorded in the subject's medical record and are submitted to Amgen. During long-term follow-up, any serious adverse event that is determined to be related to protocol-required therapy should be reported. All serious adverse events must be submitted to Amgen within 24 hours following the investigator's knowledge of the event via the Event CRF.

If the EDC system is unavailable to the site staff to report the serious adverse event, the information is to be reported to Amgen via an electronic Serious Adverse Event (eSAE) Contingency Report Form within 24 hours of the investigator's knowledge of the event. See [Appendix B](#) for a sample of the Serious Adverse Event Worksheet /eSAE Contingency Report Form.

The investigator must assess whether the serious adverse event is possibly related to the investigational product(s). This relationship is indicated by a "yes" or "no" response to the question: Is there a reasonable possibility that the event may have been caused by the investigational products. Investigational products in this study are blinatumomab and pembrolizumab.

The investigator is expected to follow reported serious adverse events until stabilization or resolution.

New information relating to a previously reported serious adverse event must be submitted to Amgen. All new information for serious adverse events must be sent to Amgen within 24 hours following knowledge of the new information. If specifically requested, the investigator may need to provide additional follow-up information, such as discharge summaries, medical records, or extracts from the medical records. Information provided about the serious adverse event must be consistent with that recorded on the Event CRF.

If a subject is permanently withdrawn from protocol-required therapies because of a serious adverse event, this information must be submitted to Amgen.

Prompt notification by the investigator to Amgen of serious adverse events is essential so that legal obligations and ethical responsibilities towards the safety of subjects and the safety of a study treatment under clinical investigation are met.

Amgen has a legal responsibility to notify both the local regulatory authority and other regulatory agencies about the safety of a study treatment under clinical investigation. Amgen will comply with country-specific regulatory requirements relating to safety reporting to the regulatory authorities, IRBs/IECs, and investigators. Amgen will comply with all international and national regulations on Suspected Unexpected Serious Adverse Reaction (SUSAR) reporting to regulatory agencies. Individual safety reports must be prepared for SUSARs according to local regulatory requirements and Amgen policy, and forwarded to investigators as necessary.

An investigator who receives an individual safety report describing a serious adverse event or other specific safety information (eg, summary or listing of serious adverse events) from the sponsor will file it along with the Investigator's Brochure and will notify the IRB/IEC, if appropriate according to local requirements.

9.2.2.3 Reporting Serious Adverse Events After the Protocol-required Reporting Period

There is no requirement to monitor study subjects for serious adverse events following the protocol-required reporting period (as defined in Section 9.2.2.2) or after end of study. However, serious adverse events **suspected to be related to IP** will be reported to Amgen, **if the investigator becomes aware of them**. In some countries (eg, EU member states), investigators are required to report serious adverse events that they become aware of after end of study. If serious adverse events are reported, the investigator is to report them to Amgen within 24 hours following the investigator's knowledge of the event.

Serious adverse events reported outside of the protocol-required reporting period will be captured within the safety database as clinical trial cases for the purposes of expedited reporting.

As the overall survival is an endpoint of this study, the investigator should report a fatal serious adverse event (regardless of causality) to Amgen with 24 hours of awareness.

9.3 Pregnancy and Lactation Reporting

If a female subject becomes pregnant, or a male subject fathers a child, while the subject is taking blinatumomab or pembrolizumab, report the pregnancy to Amgen Global Patient Safety as specified below.

In addition to reporting any pregnancies occurring during the study, investigators should report pregnancies that occur within 120 days after the last dose of protocol-required therapies.

The pregnancy should be reported to Amgen Global Patient Safety within 24 hours of the investigator's knowledge of the event of a pregnancy. Report a pregnancy on the Pregnancy Notification **Form** ([Appendix C](#)). Amgen Global Patient Safety will follow-up with the investigator regarding additional information that may be requested.

If a female subject becomes pregnant during the study, the investigator should attempt to obtain information regarding the birth outcome and health of the infant. If a male subject's female partner becomes pregnant, the investigator should discuss obtaining information regarding the birth outcome and health of the infant from the pregnant partner.

If the outcome of the pregnancy meets a criterion for immediate classification as a Serious Adverse Event (eg, female subject experiences a spontaneous abortion, stillbirth, or neonatal death or there is a fetal or neonatal congenital anomaly) the investigator will report the event as a Serious Adverse Event.

If a female breastfeeds while taking protocol-required therapies report the lactation case to Amgen as specified below.

In addition to reporting a lactation case during the study, investigators should report lactation cases that occur within 120 days after the last dose of protocol-required therapies.

Any lactation case should be reported to Amgen Global Patient Safety within 24 hours of the investigator's knowledge of event. Report a lactation case on the Lactation Notification **Form** ([Appendix C](#)). Amgen Global Patient Safety will follow-up with the investigator regarding additional information that may be requested.

10. STATISTICAL CONSIDERATIONS

10.1 Study Endpoints and Analysis Sets

10.1.1 Study Endpoints

10.1.1.1 Primary Endpoints

- Incidence of DLTs

10.1.1.2 Secondary Endpoints

- Objective response (including CR and PR) by the Lugano Classification (Cheson et al, 2014) and Revised Response Criteria (Cheson et al, 2007) during the first 12 weeks since starting blinatumomab and during the treatment period
- Complete response by the Lugano Classification (Cheson et al, 2014) and Revised Response Criteria (Cheson et al, 2007) during the first 12 weeks since starting blinatumomab and during the treatment period
- Progression free survival: will be calculated as the time from the date of first dose of blinatumomab until the date of diagnosis of progression of lymphoma, or date of death, whichever is earliest. For diagnosis of progression of lymphoma, the progression of radiographic assessment of PET/CT using Lugano Classification will be used. Subjects who are alive and did not have progression will be censored at the last radiological non-missing evaluable tumor assessment date. Progression free survival for subjects who were enrolled in dose cohorts that were not selected for the extension cohort will not be calculated.
- Overall survival: will be calculated as the time from the date of first dose of blinatumomab until death due to any cause. Subjects who are alive at the date that triggers the analysis will be censored at the date last known to be alive.
- Duration of response: calculated only for subjects who achieve an OR (ie, CR or PR) during the first 12 weeks since starting blinatumomab. The duration will be calculated from the date a response, CR or PR, is first achieved until the earliest date of a disease assessment indicating a relapse event or death, whichever occurs first. For diagnosis of progression of lymphoma, the progression of radiographic assessment of PET/CT using Lugano Classification will be used. Subjects who do not have a relapse event will be censored on their last radiological non-missing evaluable tumor assessment date. A sensitivity analysis will censor subjects who receive an autologous HSCT/allogenic HSCT at the time of autologous HSCT/allogenic HSCT unless there is no assessment after the autologous HSCT/allogenic HSCT, in which case the last assessment prior to the autologous HSCT/allogenic HSCT will be used as the censoring time.
- Blinatumomab PK parameters
- Pembrolizumab PK parameters

Note that “remission” in this context equates to “response.”

10.1.1.3 Safety Endpoints

- Incidence and severity of adverse events

10.1.1.4 Exploratory Endpoints

- Tumor PD-L1 expression will be assessed pre-treatment and on treatment to explore potential correlation with clinical outcomes
- Changes in Lymphocytes (B-cell, T-cell populations, NK cells) and leukocyte populations (leukocytes, lymphocytes, monocytes, and granulocytes) in peripheral blood
- Peripheral blood cytokine levels
- Minimal residual disease (MRD) by NGS after cycle 1 of blinatumomab

10.1.2 Analysis Sets

10.1.2.1 DLT Evaluable Analysis Set

Dose limiting toxicity evaluable analysis sets include all subjects who are DLT evaluable. To be DLT evaluable, subjects must meet one of the following criteria during DLT evaluation period:

- The subject experienced a DLT; OR
- The subject was removed from treatment for an adverse event/toxicity that is not a DLT, if the subject has been exposed to both investigational products for at least 12 days since pembrolizumab initiation with blinatumomab at the target dose; OR
- The subject was removed from treatment for reasons other than an adverse event/toxicity (ie, disease progression), and the subject has been exposed to both investigational products for at least 12 days since pembrolizumab initiation with blinatumomab at the target dose; OR
- The subject did not experience a DLT and completed the DLT evaluation period

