6.2.1.1 Blinatumomab Dosage, Administration, and Schedule

Blinatumomab is administered as a CIVI. The infusion bags will be changed by site nursing or home health care personnel trained on the protocol and on the proper administration of blinatumomab.

The first cycle of blinatumomab treatment consists of 8 weeks (56 days) of standard blinatumomab continuous infusion. Please refer to the study schema (Figure 1).

The first cycle is followed by a 28-day (\pm 3 days) blinatumomab treatment-free interval. Those subjects who do not meet criteria for discontinuation after the blinatumomab treatment-free interval may then receive a consolidation cycle of blinatumomab (cycle 2) consisting of 28 days standard blinatumomab continuous infusion. In both cycle 1 and

the consolidation cycle, the initial dose of blinatumomab will be 9 µg/day and will be dose escalated at 7-day intervals until the target dose is reached.

The dosing and schedule will be as outlined in Section 7.

The drug administration should not be interrupted, if possible. In case of infusion interruption, due to any technical or logistic reason, the interruption should be as short as possible and the infusion restarted at the earliest time possible. Every interruption longer than 1 hour should be documented. Administration of dexamethasone premedication will occur as described in Section 6.3. In case the infusion is interrupted in the first cycle and/or the second cycle, the total days at the target dose should be at least 85% of the planned days, but no more than the planned days.

A dose of up to 10% higher than the intended blinatumomab dose (per day) may not require specific intervention. In case of overdose or medication error, the infusion should be immediately stopped. Routine supportive and symptomatic care according to standard medical practice is recommended. Once the subject is stabilized and no clinically relevant safety findings due to blinatumomab are observed, resumption of blinatumomab at a correct dose can be considered after consultation with the Amgen medical monitor.

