
Subjects who have been dose reduced will have an option to re-escalate to higher dose levels within their assigned dose cohort once the adverse event has resolved to grade 1 or less for at least 7 days. (See [Appendix F](#)).

Re-start of the infusion should be performed in the hospital, under supervision of the investigator. Before blinatumomab is re-started, premedication with dexamethasone must be administered as described in [Table 6-4](#). The subject should be observed overnight for possible side effects after each restart, either in the hospital or in the outpatient setting, as applicable. When the blinatumomab infusion is re-started per [Table 6-1](#) guidelines, the schedule of assessment procedures should be repeated to align with the re-started blinatumomab dose. If re-start is at 9 µg/d then repeat schedule of assessments starting at D1. If re-start is at 28 µg/d then repeat schedule of assessments starting at D8. Refer to [Table 7-1](#) and [Table 7-2](#) for cohort Ia and [Table 7-3](#) and [Table 7-4](#) for cohort IIa/IIIa. In addition, at the start of blinatumomab cycle 2, subjects should resume the schedule of assessments following D85 to D110 procedures as outlined in [Table 7-1](#) for cohort Ia and [Table 7-3](#) for cohort IIa/IIIa (exception is for pembrolizumab specific tests which are referenced in [Table 7-2](#) and [Table 7-4](#)).

In addition to the events described above, the dose may be temporarily or permanently reduced if, by investigator's judgment, it is necessary for safety reasons.

After at least 7 days of dosing at the reduced level, the dose may be increased back to the next higher dose level. An infusion interruption of more than 14 days due to an adverse event related to blinatumomab will lead to permanent discontinuation of treatment. In case of logistical difficulties, restart of treatment can be postponed for up to 7 additional days without resulting in permanent treatment discontinuation. Treatment may be also interrupted or permanently discontinued at the discretion of the investigator if any clinical/laboratory adverse event is considered to be medically relevant.

In case of signs of cytokine release, dexamethasone must be administered orally or IV at a dose of at maximum 3 x 8 mg/day for up to 72 hours.

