Appendix E. DLT Criteria (Part 1)

All toxicities will be graded using National Cancer Institute (NCI) CTCAE Version 4.0.

The occurrence of any of the following within the dose limiting toxicity (DLT) evaluation period

- 42 days from initiation of pembrolizumab treatment (DLT period begins on day 15 for Ia and day 19 for IIa and IIIa)

will be considered a DLT, if judged by the Investigator to be possibly, probably or definitely related to study drug administration:

Laboratory DLTs	
Hematologic Toxicity	
• Any Grade 4 hematologic toxicity lasting ≥ 7 days except:
– Asymptomatic anemia not resulting in transfusion• Grade 4 thrombocytopenia lasting < 7 days if associated with:
– A bleeding event which does not result in hemodynamic instability but requires a platelet transfusion, or– A life-threatening bleeding event which results in urgent intervention and/or admission to an Intensive Care Unit
Non-hematologic Toxicity	
• Grade ≥ 3 AST or ALT• Grade ≥ 3 bilirubin• Grade 3 or 4 laboratory value except:
• Grade ≥ 3 chemistry that responds to medical intervention and resolves to grade ≤ 1 within 7 days• Grade 3 or 4 laboratory value that reoccurs
Non-laboratory DLTs	
Non-hematologic Toxicity	
• Grade 5 toxicity• Any Grade 3 or 4 toxicity except:
– Grade 3 CNS related events that resolve within 7 days with treatment interruption and routine medical management– Grade 3 CRS or tumor lysis syndrome that responds to intervention/treatment interruption and resolves to grade ≤ 1 within 7 days– Grade 3 fever, persistent for ≤ 7 days and clinically manageable by investigator discretion– Grade 3 infection, persistent for ≤ 7 days and considered controlled on anti-infective therapy by investigator discretion– Grade 3 febrile neutropenia, persistent for ≤ 7 days and considered controlled on anti-infective therapy by investigator discretion– Grade 3 vomiting, or diarrhea persistent for ≤ 3 days with optimal supportive care– Grade 3 nausea or abdominal pain persistent for ≤ 5 days with optimal supportive care

For a definition of DLT evaluable subjects, see Section 10.1.2.

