- The subject did not experience a DLT and completed the DLT **evaluation** period.

Duration of Blinatumomab/Pembrolizumab

Blinatumomab/ Pembrolizumab: For each infusion episode within a cycle, the duration of exposure will be calculated by subtracting the start date and time from the stop date and time. If either a start or stop time is missing, only the date portion will be used in calculating the duration of a specific infusion. For each cycle, the duration will be last date minus first date plus 1 of infusion. For the entire study, the duration will be the sum of the durations across cycles. The duration will be rounded to the nearest day.

Event of Clinical Interest (ECI)

Selected non-serious and serious adverse events are known as ECI and must be reported within 24 hours to the sponsor. The ECI for this trial includes

- An overdose of blinatumomab or pembrolizumab (see Protocol Section 6.2.1.1 and Section 6.2.2.1)
- Hepatic disorder (See protocol section 9.1.4)

Events of interest (EOI)

Events of interest (EOI) will be based on search strategies defined by Standard MedDRA Queries (SMQs) or Amgen MedDRA Queries (AMQs).

End of Investigational Product (IP) Administration Date

End of IP Administration for subjects who had blinatumomab or pembrolizumab is defined as the last infusion of blinatumomab/ pembrolizumab reported on the End of IP Administration CRF.

Enrollment Date

Enrollment Date is defined as the date of enrollment collected on the CRF.

Investigational Product

Amgen Investigational Product: refers to blinatumomab

Non-Amgen Investigational Product: refers to pembrolizumab

Last Dose Date of Blinatumomab/ Pembrolizumab

This is the stop date of the last infusion of blinatumomab/pembrolizumab administration reported on the Investigational Product Administration CRF.

Treatment period

Treatment period will be from study day 1 to 30 days after last dose of either blinatumomab/ pembrolizumab administration reported on the Investigational Product Administration CRF.

Prior Salvage Regimens

Prior salvage regimens are those medications recorded on the prior anti-cancer therapies CRF where the line of therapy field indicates 2nd or higher line therapy.

Relative Dose Intensity at the Target Dose

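### The completer criterion for DLT evaluability has no exposure condition, so a subject with under 12 combined target-dose days can count as a non-DLT at the cohort dose

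*Protocol*

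**What the plan says.** Protocol 10.1.2.1 gives four routes into the DLT evaluable set.

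- One is having a DLT.
- Two are for subjects removed from treatment without a DLT, whether for toxicity or for another reason. Both require that the subject was "exposed to both investigational products for at least 12 days since pembrolizumab initiation with blinatumomab at the target dose".
- The fourth is for completers: "The subject did not experience a DLT and completed the DLT evaluation period". It has no exposure condition.

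SAP 6.1 repeats the definition, including the completer route ("The subject did not experience a DLT and completed the DLT" evaluation period). The window is "42 days from initiation of pembrolizumab treatment (DLT period begins on day 15 for Ia and day 19 for IIa and IIIa" in Appendix E.

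Other provisions decide who arrives at the fourth route:

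- Appendix E excludes from the DLT list "Grade 3 CNS related events that resolve within 7 days with treatment interruption and routine medical management". It also excludes grade 3 CRS that settles to grade 1 or less within 7 days.
- Table 6-1 provides for interruption after a grade 3 event, at least 72 hours off, restart at a lower level, and stepwise return to target at 7-day intervals if the toxicity does not recur.
- Protocol 6.2.1.4.1 describes re-escalation as an option and adds that "the dose may be temporarily or permanently reduced if" the investigator judges it necessary for safety.
- Protocol 3.4 allows replacement in Part 1 only of subjects who are not DLT evaluable.
- Protocol 3.1 sets the MTD as the highest dose with a DLT in at most 1 of 6 or 2 of 10 subjects.

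**The concern.** The plan takes 12 days of combined exposure at target as the least that makes a DLT-free subject informative, but applies this only to subjects who leave treatment. A cohort IIIa subject with an exempt grade 3 neurologic event the day after the first pembrolizumab dose, whose blinatumomab is then kept below target, has about 1 combined target-dose day. That subject completes 42 days and is counted as DLT-free at 112 µg/day. A subject removed after 11 days at target is not evaluable and can be replaced.

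The DLT incidence is the primary endpoint and drives the MTD rule. An under-exposed completer adds to the denominator while having had less opportunity for a DLT at the dose being judged. The error runs one way: DLT rate down, MTD up.

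**Working it through.** **1. Planned exposure (the plan's own figure).** Cycle 1 is 56 days (protocol 6.2.1.1: "The first cycle of blinatumomab treatment consists of 8 weeks (56 days) of standard blinatumomab continuous infusion"). The target dose starts on day 8 in cohort Ia and day 15 in IIa and IIIa.

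- Ia: 56 − 7 = 49 target-dose days.
- IIa and IIIa: 56 − 14 = 42.

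Both match SAP 6.1.

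**2. Most combined target-dose days possible in the DLT window.**

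- Ia: window days 15 to 56, so 42 days.
- IIa and IIIa: window days 19 to 60, but the infusion ends on day 56, so 56 − 19 + 1 = 38 days.

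**3. One exempt event with re-escalation (Table 6-1).** Assume 3 to 7 days off, 7 days at the lower level, and no extension of the infusion. The loss is 10 to 14 days.

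- Ia: 42 − 14 = 28 to 42 − 10 = 32 days.
- IIa and IIIa: 38 − 14 = 24 to 38 − 10 = 28 days.

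All exceed 12, so this path is not affected.

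**4. Paths below 12 days.**

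- Permanent reduction, or no use of the re-escalation option, after an event on window day 1: 1 day.
- Two separate exempt events in IIa or IIIa, each costing 14 days: 38 − 28 = 10 days.

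**5. Upper bound on the effect.** The documents give no true DLT rate; assume p = 1/3. Let k under-exposed completers be unable to have a DLT. The chance of passing with at most 1 DLT in 6 is (1 − p)^m + m·p·(1 − p)^(m−1), with m = 6 − k.

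| k | at most 1 of 6 | at most 2 of 10 |
|---|---|---|
| 0 | 256/729 = 0.351 | 0.299 |
| 1 | 112/243 = 0.461 | 0.377 |
| 2 | 48/81 = 0.593 | 0.468 |

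The last column is the corresponding binomial probability of at most 2 events in 10 − k subjects. At other assumed rates, P(at most 1 of 6) for k = 0, 1, 2 is 0.233, 0.337, 0.475 at 40% and 0.109, 0.188, 0.312 at 50%.

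**6. A less extreme assumption.** Take a constant DLT hazard at target and none below it, with 1/3 as the risk over 38 days. A subject with d days then has q = 1 − (2/3)^(d/38). With five fully exposed subjects, P(at most 1 of 6) = 0.461 − q × 80/243.

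- d = 24 to 28: q = 0.226 to 0.258, giving 0.387 to 0.376.
- d = 11: q = 0.111, giving 0.424.
- d = 1: q = 0.011, giving 0.457.

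The bound is therefore close for a subject with almost no exposure, and well above the effect for one who returned to target.

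**7. Effect on an observed rate.** Take 1 DLT in 6, with one further subject an under-exposed completer.

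- As defined: 1/6 = 16.7%.
- Without that completer: 1/5 = 20.0%.
- With that completer as an event: 2/6 = 33.3%, which fails the MTD rule.

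**The case against.** - **A completer has been watched for the full 42 days, whereas a removed subject may not have been.** This is a fair reason for treating the routes differently, and related toxicity at a reduced dose still counts as a DLT. It does not show that the subject was observed on the dose the cohort is meant to test.
- **Table 6-1 directs a return to target, and protocol 6.2.1.1 says target-dose days after an interruption should reach 85% of plan.** A reader might infer from the completer criterion that any subject rescued by interruption and dexamethasone barely received the target dose. Step 3 does not support that: near-zero exposure needs a permanent reduction or an unused option. But the 85% statement is per cycle, worded as a recommendation and not linked to evaluability. SAP 10.6.8 uses 85% only to define a completed cycle.
- **Frequency.** A reader might take the protocol's 21.7% and 26.1% for grade 3 or higher neurologic events as showing that 1 affected subject in 6 is to be expected. They do not. They come from monotherapy and are not limited to the DLT window; the reported median onset is 18 days, before the window opens in IIa and IIIa. They also include grade 4 and longer-lasting events, which the exemption does not cover.
- **Some such subjects may count as removed.** Table 6-3 has permanent pembrolizumab discontinuation for grade 3 immune-related neurological toxicity. The definition does not say whether stopping one drug is removal from treatment, so this is unresolved.
- **The DLRT may use clinical judgement and the totality of the data.** True, but this leaves the denominator of the reported rate unchanged.
- **Making these completers non-evaluable and replacing them would drop their intolerance from the rate.** This stands, and it shapes the fix.

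**Conclusion.** The gap is real. Both removal routes carry a 12-day exposure condition, the completer route carries none, and no other provision ties exposure to evaluability. The written rules allow an under-exposed completer to count as a non-DLT in the primary rate and the MTD rule, and protocol 3.4 does not allow that subject to be replaced.

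The effect is limited to completers with under 12 combined target-dose days. For one such subject in six, the chance of passing rises from 0.351 to at most 0.461 at an assumed true rate of 1/3; for two, to at most 0.593. These bounds rest on that assumed rate and on no DLT being possible in affected subjects. The documents do not say how many such subjects there are. It would go too far to conclude that the DLT rate or MTD is in fact wrong, or that subjects on the single-event path are miscounted.

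SAP section 11 states that Part 2 will not proceed, so what is at stake is the Part 1 MTD conclusion and the reported DLT rate.

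**What to change.** Reconcile the completer criterion in protocol 10.1.2.1 and SAP 6.1 with the 12-day condition in the two removal criteria, either by applying the condition or by stating why completion alone is enough. State also whether stopping one drug counts as removal from treatment.

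Add to SAP 10.6.1:

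- A listing for each subject of combined target-dose days in the DLT window, with the reason for any shortfall.
- Each cohort's DLT rate with exact confidence interval:
  - (a) as now defined;
  - (b) excluding completers with under 12 combined days at target;
  - (c) counting as events those completers whose under-exposure was due to treatment-related toxicity, so that their intolerance stays in the rate.
- A statement of whether the MTD conclusion holds under each. Under (b) the denominator may no longer be 6 or 10, the only sizes the rule covers; say so where it happens.

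Label (b) and (c) as sensitivity analyses, since they would be added late. The cost is a smaller denominator in (b) and a little programming. Protocol 6.2.1.1 already has dose and start and stop times recorded on the CRF, and SAP 10.6.8 already summarises dose modifications with reasons. This changes an analysis set and its reporting; no dose or treatment rule is proposed.
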